#### Attachments

Attach Type	File Name
Advertising	PATH Home Recruitment Flyer - PR Approval.pdf
Advertising	V5 clean 74853_Advertising_488609-111_24_2021.docx
Advertising	TC V4 74853_Advertising_488609-1.docx

## Research Procedures

Describe how the research will be conducted.

- What experience will study participants have?
- What will study participants be expected to do?
- How long will the study last?
- Outline the schedule and timing of study procedures.
- Provide visit-by-visit listing of all procedures that will take place.
- Identify all procedures that will be carried out with each group of participants.
- Describe deception and debrief procedures if deception is involved.

Differentiate between procedures that involve standard/routine clinical care and those that will be performed specifically for this research project. List medications that are explicitly forbidden or permitted during study participation.

Local staff at each of the 11 sites will be trained as Perinatal Nurse Facilitators, with local residents being trained as peer support specialists. All study participants will receive regular prenatal care through their community based obstetric providers and medication assisted treatment (MAT) with buprenorphine or methadone for opioid use disorder through their respective licensed prescribing providers. In addition to PNC and MAT, study patients will receive a rotating supplementary patient education curriculum (see below) based on the PATHways intervention for OUD in pregnancy. The method by which this will be delivered is based on their allocation into the "group" or "telemedicine" arm of the trial. Half of the participating clusters will be randomized to receive the patient education curriculum through a local group care model imparted through a perinatal nurse facilitator and community based peer support specialist. The remaining clusters will receive the augmented clinical care through telemedicine provided by a Perinatal nurse educator, substance abuse counselor and/or Peer Support Specialists. The research and intervention procedures are identical for participants regardless of their criminal justice status.

Potential perinatal nurse facilitators will be identified at each study site randomized to the "group" arm. These individuals will undergo a two day training program with the UK-PATHways: Hub Perinatal Nurse Facilitator ([name] - see key personnel). [name] will serve as a point person for study site Nurse Facilitators and lead monthly meetings via skype or in person. Peer support specialists will be identified within the region (3 total), and, if not previously certified/trained, training will be provided.

Telemedicine arm consultations will be provided by study personnel identified within this application including [name], [name] and [name].

**GROUP CARE ARM:** Study participants at the clusters randomized to the "group" arm will receive group care at 2 week intervals initiated from study enrollment. Group care sessions will be led by an on-site perinatal nurse facilitator and a local peer support specialist. The prenatal group sessions will be imparted in a structured fashion with each session lasting for 45-60 minutes. The content matter discussed will follow a rotating curriculum comprising 8 core sessions over a 16 week period, and will be repeated at each study site as long as there are enrolled active study patients. Once a patient is 8 weeks postpartum ,she will be seen monthly until 6 months postpartum. Data will be collected at each visit by trained study site personnel and entered in a secured online database (REDCap).

**TELEMEDICINE ARM:** Study participants at the clusters randomized to the telemedicine arm will receive the intervention through a telemedicine platform as part of the Kentucky Angels telemedicine program. The division of maternal fetal medicine has established a platform for obstetric outreach addressing perinatal issues pertaining to high risk pregnancies across Kentucky. As part of this cluster RCT, participants at study sites randomized to this arm will receive these telemedicine-based consultations with providers from perinatal nurse educators, peer support specialists, and substance abuse counselors at the University of Kentucky every two weeks until 8 weeks postpartum - and then monthly until 6 months post-partum. Should the patient have the need for additional sessions with a specialist, these will be provided . Data will be collected at each visit by trained study site personnel, and entered into a secured online database (REDCap). See data management plan for more information on the data storage.

The supplemental clinical care that patients will consist of a standardized rotating 8 topic patient education curriculum, including the following topics: 1. Treatment Options for Opioid Use Disorder 2. Smoking Cessation 3. Relapse Prevention Education 4. NAS Reduction Education 5. Breast Feeding Support/Education 6. Domestic Violence Education 7. Postpartum Depression 8. Birth Control/Family Planning.

### Attachments

## Data Collection & Research Materials

In this section, please provide the following:

- Describe all sources or methods for obtaining research materials about or from living individuals (such as specimens, records, surveys, interviews, participant observation, etc.), and explain why this information is needed to conduct the study.
- For each source or method described, please list or attach all data to be collected (such as genetic information, interview scripts, survey tools, data collection forms for existing data, etc.).
- If you will conduct a record or chart review, list the beginning and end dates of the records you will view.

We will be performing the following maternal patient surveys at the following study time-points:

## SCHEDULE OF STUDY ASSESSMENTS

## ENROLLMENT/INTAKE

1. DSM-5 Criteria for Opioid Use Disorder
2. Edinburgh Depression Scale
3. Fagerstrom Nicotine Dependence
4. GAD-7 (Anxiety)
5. Adverse Childhood Experience (ACE)
6. Abuse Assessment Screen

## 3rd Trimester

- 1) WHO QoL-BRF (Quality of Life measure)
- 2) Experience of Care and Health Outcomes (ECHO) - modified
- 3) Cornell Health Services Index (CHSI)
- 4) Fagerstrom Nicotine Dependence
- 5) Edinburgh Depression Scale
- 6) GAD-7

## 3 months Post-Partum

- 1) WHO QoL-BRF
- 2) Experience of Care and Health Outcomes (ECHO) - modified
- 3) Cornell Health Services Index (CHSI)
- 4) Fagerstrom Nicotine Dependence
- 5) Edinburgh Depression Scale
- 6) GAD-7
- 7) Ages and Stages

## 6 months Post-Partum

- 1) WHO QoL-BRF
- 2) Experience of Care and Health Outcomes (ECHO) - modified
- 3) Cornell Health Services Index (CHSI)
- 4) Fagerstrom nicotine Dependence
- 5) Edinburgh Depression Scale
- 6) GAD-7
- 7) Ages and Stages

Study participants will be asked to complete surveys in REDCap available on iPads dedicated specifically for this project; however, all participants will have the option to complete hard copies of the surveys if they prefer. Data from surveys completed on iPads will be uploaded directly into REDCap. Devices will be managed by UK Healthcare IT, which already deploys a large number of iPad devices and is very familiar with the security and management requirements of iOS based devices. UK Healthcare IT currently has a management app configured to ensure the security of the devices and to apply sufficient restrictions that the devices cannot be used for unintended purposes. All devices will be stored securely in locked cabinets.

We will be collecting the following maternal data:

1. Prenatal labs
2. Infectious complications
3. MAT program participation rate (by patient)
4. Study program participation rate (e.g. frequency of clinic attendance at telemedicine and/or group sessions);
5. Prenatal care attendance (medical record review).
6. Urine drug screen result on admission to labor and delivery, 3 and 6 months postpartum (obtained from medical records)
7. Smoking status: evaluated through patient interview and Fagerstrom Nicotine Dependence Scale at intake, 3rd trimester, 3 and 6 months postpartum.
8. Addiction severity: DSM-5 Criteria for Opioid Use Disorder at intake
9. Obstetric complications including but not limited to Preterm birth <37 GA, growth restriction (<10%ile), preterm rupture of membranes, preeclampsia, multiple gestation, gestational diabetes, chorioamnionitis, miscarriage, fetal demise, cesarean delivery (medical record review)
10. Overdose tracking (overdose reversal agent needed, admitted to hospital/ED for overdose): patient interview at every visit
11. Health services utilization: Cornell Health Service Index administered in 3rd trimester, 3 and 6 months post-partum
12. Patient experience of care: Experience of Care and Health Outcomes (modified) Survey administered in 3rd trimester, 3 and 6 months post-partum
13. Depression: Edinburgh Postpartum Depression Scale administered at intake, 3rd trimester, 3 and 6 months postpartum
14. Anxiety: GAD7 administered at intake, 3rd trimester, 3 and 6 months postpartum
15. Quality of life: WHO QoL-BRF administered in 3rd trimester, 3 and 6 months post-partum
16. Mother-Infant dyad status/Foster care requirement: retention of custody evaluated by patient interview at hospital discharge, 3 and 6 months postpartum
17. Maternal breastfeeding status: evaluated by patient interview at delivery, 3 and 6 months postpartum.

We will be collecting the following fetal data:

Fetal size per gestational age; Any genetic or structural anomalies; any other fetal complications.

We will be collecting the following neonatal data, including the following assessments:

Gestational age and weight at birth; 5 & 10min Apgar score; NICU/nursery hospital admission; NAS diagnosis & treatment requirement (primary outcome); NAS medication days; in-hospital growth (birth to discharge per day); other infant morbidities; total hospitalization length of stay; immunization compliance, ED visits, follow up with scheduled pediatric visits.

Data will be obtained via medical record review, patient interview, physician/staff report, review of state Medicaid data, and hospital discharge data by the study site research staff with the oversight of the UK-study team.

We will perform fidelity monitoring of intervention delivery. Research nurses/facilitators (group arm), providers (telemedicine arm), and all study participants will be asked to complete a fidelity form, similar to an evaluation form, at the end of each educational session. We will evaluate intervention fidelity by comparing provider and participant responses. If any discordance is identified between provider and participant responses for a given topic, additional training related to intervention delivery may be required.

In each arm, patients will be randomly selected to participant in a qualitative interview process at each participating site at the time of the 6 month postpartum follow-up. The interviews will be facilitated by Co-I [name], who has extensive experience using qualitative techniques with substance-involved patients in community based and treatment settings, with the assistance of research coordinators trained in qualitative interviewing techniques. Patients will be offered a fifty dollar stipend for their time to participate in the interview. 3 patients will be randomly selected from each participating site for a total of 33 interviews.

In addition, we will perform in-depth qualitative interviews (also by Co-I [name]) of both physician and research nurses from each site at study conclusion in order to evaluate the acceptability of the study intervention in the practice setting.

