**Background**

Include a brief review of existing literature in the area of your research. You should identify gaps in knowledge that should be addressed and explain how your research will address those gaps or contribute to existing knowledge in this area. For interventional research, search PubMed and ClinicalTrials.gov for duplicative ongoing and completed trials with same condition and intervention(s).

Perinatal opioid use disorder (OUD) is a major health concern in the US with significant impact on mothers, infants, and communities. Our team at University of Kentucky/UK HealthCare (UK) has developed a comprehensive clinical care model for perinatal OUD (known as UK-PATHways) that has demonstrated success in maternal and neonatal outcomes. The overreaching goals of the proposed project are to 1) expand the reach of this successful clinical program, 2) to reduce the impact of perinatal OUD in underserved rural areas of our state, and 3) to compare the relative effectiveness methods of delivery active elements of the PATHways program for rural implementation (local group-support vs. telemedicine). The UK-PATHways program preliminary successes during the first three years are clear: enrolled mothers (n>200) have reduced relapse, increased treatment compliance, and improved neonatal outcomes when compared to non-enrolled OUD mothers. However, at this time UK-PATHways is only available at our main healthcare campus in Lexington, KY. Many eligible patients reside great distances from our clinical home and some current patients travel hours to access this valuable resource. While Medication Assisted Therapy (MAT) has become increasingly available in our region, many of the components of the UK-PATHways program are not readily accessible in rural Central and Eastern Kentucky and the quality of programming with MAT treatment is not standardized in these locations. Furthermore, rural patients continue to face challenges related to stigma of their OUD and transportation difficulties if they desire more comprehensive services. The proposed study will evaluate the introduction of essential components of the UK-PATHways program into rural communities, and identify the optimal intervention strategies for expansion of services and to improve the treatment of OUD for rural patients.

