## **Statistical Analysis Plan NCT03725332**

To begin, continuous variables (gestational age at birth, neonatal weight, infant hospitalization length of stay, etc.) will be summarized with descriptive statistics (n, mean, standard error, first and third quartiles, and minimum and maximum); categorical variables (NAS treatment required, mother-infant dyad status, preterm birth, maternal smoking status, etc.) will be summarized with counts and percentages. To investigate differences in outcomes between treatment arms, a generalized linear mixed model will be performed. Mixed models allow for additional flexibility to control clustering while controlling for covariates such as socioeconomic status, race, age, addiction severity, if needed. Results will be presented with means (standard error) by treatment arm. Note that the primary outcome requires a noninferiority analysis; the secondary outcomes require superiority analysis to identify between-group differences. Mixed model assumptions will be assessed using plots of each outcome, diagnostics, and/or residual plots. If deviations from distributional assumptions are identified, remedial measures will be deployed as needed. In the case that methods assumptions are not satisfied, remedial measures (eg, variable transformations, nonparametric methods) will be employed.

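### No urine drug screen is itemised at intake, so the delivery, 3- and 6-month screens cannot be adjusted for their own baseline; the main loss is precision

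*Combined protocol and SAP*

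**What the plan says.** In the protocol, under Data Collection & Research Materials, item 6 of the maternal data list reads "Urine drug screen result on admission to labor and delivery, 3 and 6 months postpartum (obtained from medical records"). All three times fall after the intervention has begun, because sessions start at enrolment (Study Design; Research Procedures).

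The Enrollment/Intake list in the Schedule of Study Assessments has one opioid-specific instrument, "DSM-5 Criteria for Opioid Use Disorder", and no drug screen. The maternal data list gives the same instrument as its severity measure: "Addiction severity: DSM-5 Criteria for Opioid Use Disorder at intake". Item 1 of that list is prenatal laboratory results, with no content or timing stated.

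Other measures do have a baseline, for example "Smoking status: evaluated through patient interview and Fagerstrom Nicotine Dependence Scale at intake, 3rd trimester, 3 and 6 months postpartum". Depression and anxiety are also measured at intake and again at follow-up.

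The SAP specifies a generalized linear mixed model that can adjust for "covariates such as socioeconomic status, race, age, addiction severity, if needed". It does not name the baseline value of any outcome as a covariate.

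**The concern.** Drug use is something the programme sets out to change. Relapse prevention is one of the eight curriculum topics, and the Background reports of the parent programme that "enrolled mothers (n>200) have reduced relapse, increased treatment compliance, and improved neonatal outcomes when compared to non-enrolled OUD mothers". The urine screen is the only laboratory measure of maternal drug use that is itemised. The other drug-related follow-up item is "Overdose tracking (overdose reversal agent needed, admitted to hospital/ED for overdose): patient interview at every visit", which records only severe events.

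Women enter at 6 to 32 weeks with a history of opioid use disorder and current medication treatment. Abstinence at entry is not required. A positive screen at delivery may therefore be use that was already present at enrolment, or use that began later, and the itemised data do not separate the two.

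There are also few randomised units. The site count is 12 in some sections (Study Population, Study Design, Subject Recruitment) and 11 in others (Research Procedures, Resources), and allocation is stratified only by delivery volume. Sites are described as already randomised (Prisoners, Section 1), while site nurses identify and approach women and participants may be paid for referrals (Payment). Who enters each arm could thus differ in a way that randomising sites does not control. Without a baseline screen such a difference would be hard to see, and could be adjusted for only through proxies.

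**Working it through.** **1. What has a baseline and what does not**

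| Measure | Intake | Follow-up |
|---|---|---|
| Smoking | yes | 3rd trimester, 3 and 6 months |
| Depression, anxiety | yes | 3rd trimester, 3 and 6 months |
| DSM-5 severity | yes | none listed |
| Urine drug screen | none listed | delivery, 3 and 6 months |

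**2. How large a chance imbalance could be**

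The documents give no power calculation, intracluster correlation (ICC) or screen-positive rate, so there is no figure of the plan's own to reproduce. What follows is an illustration.

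Inputs from the documents:
- maximum of 267 subjects
- 12 sites (11 in some sections), allocated 1:1

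Assumptions:
- The 267 are all women. The planned-enrolment table totals 15 + 15 + 503 = 533, close to 2 × 267, which would fit mothers plus infants, but the documents do not say so.
- Sites are of equal size.
- Baseline positivity p is 0.2 to 0.4.
- The ICC is 0.01 to 0.10.

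Formulae, with m women per site:
- m = 267/12 = 22.25
- design effect DE = 1 + (m - 1) × ICC
- SE of the between-arm difference = sqrt[p(1 - p) × DE × (1/133.5 + 1/133.5)]
- chance of an imbalance of at least 10 points = 2 × [1 - Φ(0.10/SE)]

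Results with 12 sites:
- p = 0.2, ICC = 0.01: DE = 1 + 21.25 × 0.01 = 1.21; SE = sqrt(0.16 × 1.2125 × 0.01498) = 0.054; chance 6%.
- p = 0.3, ICC = 0.05: DE = 2.06; SE = sqrt(0.21 × 2.0625 × 0.01498) = 0.081; chance 21%.
- p = 0.4, ICC = 0.10: DE = 3.12; SE = sqrt(0.24 × 3.125 × 0.01498) = 0.106; chance 35%.

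The corresponding 95% ranges (1.96 × SE) are about ±11, ±16 and ±21 points. With 11 sites the chance runs from about 7% to 36%.

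**3. What that means at follow-up**

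Suppose the baseline-to-follow-up correlation is r = 0.3 to 0.7 (assumed). A 10-point baseline imbalance then goes with a shift of r × 10 = 3 to 7 points in the unadjusted follow-up difference.

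If follow-up has the same p = 0.3 and ICC = 0.05, the SE of the follow-up difference is itself 8.1 points. The shift is part of that sampling error and does not come on top of it.

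**4. What adjustment could recover**

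On a linear scale, with the same r between sites and within them, adjustment multiplies the variance by 1 - r²: 0.91, 0.75 and 0.51 for r = 0.3, 0.5 and 0.7. An SE of 8.1 points becomes 8.1 × sqrt(0.91) = 7.7, 8.1 × sqrt(0.75) = 7.0 and 8.1 × sqrt(0.51) = 5.8. The real gain would be smaller, because some women will have no baseline screen.

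**The case against.** The case on the other side is substantial, and most of it stands.

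- **Some adjustment is possible.** A reader might infer that an imbalance could not be corrected at all. The documents do not support that: severity is collected at intake and named in the SAP, whose covariate list is open-ended. It is a partial proxy, because it measures the disorder and not current use, and the SAP leaves its use optional.
- **An early screen may already be collected.** Prenatal laboratory results are gathered without stated content. The Records, Privacy, and Confidentiality section describes open-ended abstraction on the course of the disorder and of medication treatment in pregnancy. The documents show only that no dated intake screen is itemised.
- **No relapse endpoint is promised.** The screen is a collected item. No section labels it an outcome or defines relapse, and Aim 2 does not list the secondary outcomes. The plan breaks no commitment here. The screen still bears on the analysis if it is among the secondary outcomes that the SAP tests for superiority.
- **Chance imbalance is not bias.** A follow-up comparison of randomised sites is unbiased in expectation, and a standard error that accounts for clustering already covers chance differences. This is correct. It does not cover differences in who is recruited after sites are allocated.
- **The primary outcome.** A reader might extend the point to neonatal abstinence syndrome. The documents give nothing that links a screen taken at 6 to 32 weeks to that outcome, and use near birth is already captured by the delivery screen.

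**Conclusion.** The point holds in a limited form. Item 6 itemises no intake screen. From the listed data, the follow-up screens therefore cannot be adjusted for their own baseline, and a positive result cannot be classed as continued or new use. The main loss is precision, together with the means to detect and adjust for baseline differences, including any from recruitment after site allocation.

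The size rests wholly on assumed inputs. With 12 sites, positivity of 20-40% and an ICC of 0.01-0.10, a 10-point imbalance has a chance of roughly 6-35%. The possible reduction in standard error depends on an assumed correlation. Nothing here shows a numerical error in the plan, a biased comparison or a threat to the primary analysis. The change is still worth making because it is cheap and uses records already under review.

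**What to change.** 1. Add to item 6 the most recent urine drug screen before the first session, within a look-back window fixed in advance. Abstract it from the prenatal or medication-treatment records already reviewed, and order no new test. Apply one definition of a positive screen at all four times, stating how prescribed buprenorphine or methadone is handled.
2. Report the result by arm and by site, including the share not done.
3. In the SAP, prespecify it as a covariate (positive / negative / not done) in the mixed models for the delivery, 3- and 6-month screens.
4. Add a sensitivity analysis without this covariate. Whether a screen was done may follow site practice, and with so few sites the not-done category could partly stand in for site.
5. In the model for neonatal abstinence syndrome, use it in a sensitivity analysis at most.

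The cost is one more abstracted value per woman and a few lines in the SAP. It can be done retrospectively for women already enrolled, where a record exists. The drawbacks are that routine testing is not standardised across sites and that some values will be missing.

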**SUBJECT DEMOGRAPHICS**

0 unresolved comment(s)

Age level of human subjects: (i.e., 6 mths.; 2yrs., etc.)  to **Study Population:**

Describe the characteristics of the subject population, including age range, gender, ethnic background and health status. Identify the criteria for inclusion and exclusion.

Provide the following information:

- A description of the subject selection criteria and rationale for selection in terms of the scientific objectives and proposed study design;
- A compelling rationale for proposed exclusion of any sex/gender or racial/ethnic group;
- Justification for the inclusion of vulnerable groups such as children, prisoners, adults with impaired consent capacity, or others who may be vulnerable to coercion or undue influence.

Please consider these resources:

[NIH Diversity Policy](#)

[FDA Diversity Guidance](#) 

Pregnant women at 6 to 32 weeks' gestational age with a history of OUD (as defined by the DSM-5) who are receiving MAT (with either buprenorphine based products or methadone) and obtaining prenatal care at one of twelve study sites. Study sites are located throughout Central and Eastern Kentucky and have an established relationship with the University of Kentucky through an existing telemedicine network called the Kentucky Angels network.

Study sites include:

1. Ashland, KY - Karen's Place Maternity Center, ARC
2. Bowling Green, KY: Fairview Community Health Center
3. Corbin, KY: Grace Community Women's Health
4. Georgetown, KY: Brightview Health, LLC
5. Georgetown, KY: UK Women's Health Obstetrics and Gynecology – Georgetown
6. Louisville, KY: University of Louisville, HCCP/Prenatal Clinics
7. Middlesboro, KY: ARH Women's and Family Health Center-Middlesboro
8. Morehead, KY: UK Morehead Women's Healthcare
9. Prestonsburg, KY: Frontier Behavioral Health Center, PLLC
10. South Williamson, KY: ARH Women's and Family Health Center - Tug Valley
11. Vico, KY: Primary Care Centers of Eastern Kentucky
12. Pikeville, KY - Pikeville Medical Center

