providers and medication assisted treatment (MAT) with buprenorphine or methadone for opioid use disorder (OUD) through their respective licensed prescribing providers. In addition to PNC and MAT, study patients will receive supplementary clinical care every two weeks either in the form of a structured group model (GROUP CARE) or in a telemedicine consult (TELEMEDICINE) for OUD in pregnancy through their allocation into the "group" or "telemedicine" arm of the trial. Half of the participating clusters will be randomized to receive group prenatal care ("group" arm) imparted through a perinatal nurse facilitator and community based peer support specialist. The remaining clusters will receive pregnancy specific education through telemedicine imparted by a Perinatal nurse educator, substance abuse counselor and/or Peer Support Specialists. The supplemental clinical care that patients will consist of a standardized rotating 8 topic patient education curriculum, including the following topics: 1. Treatment Options for Opioid Use Disorder 2. Smoking Cessation 3. Relapse Prevention Education 4. NAS Reduction Education 5. Breast Feeding Support/Education6. Domestic Violence Education 7. Postpartum Depression 8. Birth Control/Family Planning.

Meetings and consultations will occur every two weeks in each arm of the trial from enrollment until 8 weeks post-partum and will then continue monthly until 6 months post-partum.

Potential Perinatal Nurse Facilitators will be identified at each study site randomized to the "group" arm. These individuals will undergo a two-day training program with the UK-PATHways: Hub Perinatal Nurse Facilitator ([name], see key personnel). The UK-PATHways: Hub Perinatal Nurse Facilitator will serve as a point person for study site Nurse Facilitators and lead monthly meetings via Skype or in person. Peer Support Specialists will be identified within the region (three total) and, if not previously certified/trained, training will be provided.

Telemedicine arm consultations will be provided by study personnel identified within this application including [name], LMFT, [name] and [name].

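### Visit interview is the only source named for overdose, so the count can differ between arms if attendance or dropout differs

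*Combined protocol and SAP*

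**What the plan says.** The maternal data list in the Research Description, under Data Collection & Research Materials, gives the overdose item as "Overdose tracking (overdose reversal agent needed, admitted to hospital/ED for overdose): patient interview at every visit". Other items in that list name a record source: prenatal care attendance (item 5), obstetric complications (item 9), and item 6, which reads "Urine drug screen result on admission to labor and delivery, 3 and 6 months postpartum (obtained from medical records".

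After the maternal, fetal and neonatal lists, a separate paragraph gives the sources in general: "Data will be obtained via medical record review, patient interview, physician/staff report, review of state Medicaid data, and hospital discharge data". It does not say which items use which source.

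The visits are the intervention contacts. Under Study Design, "Meetings and consultations will occur every two weeks in each arm of the trial from enrollment until 8 weeks post-partum"; they are then monthly to 6 months. Research Procedures adds that data are collected at each visit. Item 4 records participation, for example "frequency of clinic attendance at telemedicine and/or group sessions".

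No recall window for the overdose question is stated, and no rule for missed visits or loss to follow-up. The SAP neither names overdose nor gives a missing-data rule.

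**The concern.** An overdose that is found only by asking the woman needs a later attended contact to be counted. The two arms deliver the same curriculum in different ways, so attendance or dropout could differ between them. The arm that keeps women in contact would then have more of its overdoses counted, and the arm that loses them could look safer for that reason alone. A fatal overdose, or one after the last contact, cannot be reported at interview in either arm.

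At stake is a serious maternal harm. The hospital or ED part of item 10 is something that records can show whether or not the woman attends.

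**Working it through.** The plan has no figure to reproduce: it gives no overdose rate, attendance rate, dropout rate or recall window. What follows is illustration. All rates are assumed, and the true overdose rate is the same in both arms, so any ratio other than 1 comes from ascertainment.

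**Formula.** Observed rate = true rate × probability of capture. With equal true rates, the apparent ratio is the capture in the better-retained arm divided by that in the other.

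**Number of visits.** The population is "Pregnant women at 6 to 32 weeks' gestational age with a history of OUD". Assume delivery at 39 weeks. Fortnightly visits to 8 weeks postpartum number (39 − 6 + 8)/2 = 20.5, so 20, for enrolment at 6 weeks, and (39 − 32 + 8)/2 = 7.5, so 7, for enrolment at 32 weeks. Four monthly visits bring the totals to 24 and 11. The look-back case below assumes 18.

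**Case A: each interview covers only the interval before an attended visit.** Capture = attendance.
- 80% vs 60%: 0.80/0.60 = 1.33
- 90% vs 70%: 0.90/0.70 = 1.29
- 70% vs 60%: 0.70/0.60 = 1.17

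**Case B: each interview looks back to the last attended visit, and misses are sporadic and independent.** An event is lost only if every remaining visit is missed. Capture is the mean of 1 − (1 − a)^m over m = 1 to 18 remaining visits, where a is attendance.
- a = 0.80: (18 − 0.25)/18 = 0.986
- a = 0.60: (18 − 0.667)/18 = 0.963
- Ratio: 0.986/0.963 = 1.02
- With 11 visits: 10.75/10.333 = 1.04. With 24 visits: 23.75/23.333 = 1.02.

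**Case C: look-back, with permanent dropout spread evenly over follow-up.** For a dropout proportion d, capture = 1 − d/2.
- 10% vs 30%: 0.95/0.85 = 1.12
- 20% vs 40%: 0.90/0.80 = 1.125

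**Scale of case A.** The application allows at most 267 subjects, about 133 per arm. At an assumed true rate of 10% and attendance of 80% vs 60%, the expected counts are 133 × 0.08 = 10.6 and 133 × 0.06 = 8.0. Ignoring clustering, the standardised difference is 0.02/√(2 × 0.07 × 0.93/133) = 0.64. The chance of a nominally significant excess at two-sided 0.05 is then about 9%, against 2.5% in that direction without the bias. A true ratio of 0.60/0.80 = 0.75 in favour of the better-attending arm would be exactly cancelled.

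**Adding records in both arms to case A (80% vs 60%).** Let f be the fraction of overdoses reaching hospital or ED and s the fraction of those that records find. If records and interview find events independently, capture = 1 − (1 − a)(1 − f·s).

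| f | s | Capture at 80% | Capture at 60% | Ratio |
|---|---|---|---|---|
| 0.5 | 0.80 | 0.880 | 0.760 | 1.16 |
| 0.5 | 0.95 | 0.895 | 0.790 | 1.13 |
| 0.8 | 0.80 | 0.928 | 0.856 | 1.08 |
| 0.8 | 0.95 | 0.952 | 0.904 | 1.05 |
| 1.0 | 0.80 | 0.960 | 0.920 | 1.04 |
| 1.0 | 0.95 | 0.990 | 0.980 | 1.01 |

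Records shrink the distortion in every row. What remains comes from events that never reach care or that the records miss.

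**The case against.** The strongest reply is that the plan never excludes records for overdose. The general source paragraph can be read as covering the maternal items. Records, Privacy, and Confidentiality says that details of the course of OUD in pregnancy are abstracted from the electronic record. Data and Safety Monitoring says the same of maternal perinatal data and adds adverse events, self-reported and verified by staff. This stands in part. A reader might infer that overdose is counted by interview alone, and the documents do not support that. But none of these sections assigns records to item 10 or says that they will be searched for women who have stopped attending.

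A reader might also infer that the better-attending arm will look worse. That too is unsupported. The visit schedule is the same in both arms, no expected attendance is given, and a real benefit could offset the distortion.

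Nor does missing sessions mean that a woman is never asked. The Payment section sets paid data-collection points at 28–32 weeks, delivery, 3 months and 6 months. The prisoner section (Condition 5) says follow-up is combined with clinical visits where possible. Only complete loss of contact removes her from interview. That non-attenders are at higher risk is plausible, but the documents do not say so.

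Finally, interview may be the only way to learn of a reversal outside hospital. That stands, and it argues against making records the main count.

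**Conclusion.** The point holds as a gap in assigned sources. Interview at visits is the only source item 10 names, so ascertainment can differ between arms if attendance or dropout differs, and fatal overdoses or those after the last contact would be missed. With equal true rates, the apparent ratio is about 1.02 (80% vs 60% attendance, look-back), 1.12 (dropout 10% vs 30%) or 1.33 (80% vs 60%, no look-back). The plan does not say which case applies, and the rates are assumptions.

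A stronger reading, that the trial's conclusions are biased, is not supported. The primary outcome is NAS and its analysis is unaffected. The SAP does not name overdose as a primary or secondary outcome. The effect is on a collected maternal safety measure.

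**What to change.** 1. In item 10, assign the medical record, hospital discharge and Medicaid sources already listed to the hospital/ED component, for every enrolled woman from enrolment to 6 months postpartum, regardless of attendance.
2. Keep interview for reversal-agent use, and have it cover the whole period since the last contact. This moves the interview part from case A towards case B.
3. Report record-ascertained and interview-only events separately as well as combined, by arm.
4. State how missed visits and loss to follow-up are handled for this item.

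The cost is a change of wording and a small amount of extra abstraction. It is somewhat more if the sponsor meant the Medicaid and discharge sources for infants only, because maternal data would then have to be added to the request. Two limits remain: community reversals that never reach care still depend on interview, and a fatal overdose without hospital or ED contact may still be missed.
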